3.5.6 Physical Examinations

All abnormal physical examination findings, including details of any abnormalities will be listed by patient.

3.6 Data Safety Monitoring Board

An independent Data Safety Monitoring Board (DSMB) will be convened for this study to routinely monitor patient safety and evaluate pre-specified interim analyses to stop the study early. The DSMB will receive summary reports of all SAEs including unexpected SAEs. A DSMB charter, detailing all aspects of the DSMB's composition, scope of review, and procedures will be provided in a separate document. An unblinded statistician will be assigned to the DSMB. This statistician will not be involved in any aspects of study conduct outside of the DSMB, and their role will be defined in the DSMB charter.

A review by the DSMB will be done when approximately 25 to 35 patients in the OL cohort have completed 30 days of treatment. At this time, an assessment of benefit, risk, and endorsement to proceed to Phase 3 will be undertaken.

Appendix 1 Analysis Visit Windows

Table 1. Analysis Visit Windows for Quality of Life Data

Nominal Visit	Nominal Study Day	Visit Window Study Day	
		Lower Limit	Upper Limit
Day 1/Baseline	1	1	1
Week 4	29	2	43
Week 8	57	44	71
Week 12	85	72	92
Week 14	99	93	113
Week 18	127	114	141
Week 22	155	142	169
Week 26	183	>169	

Table 2. Analysis Visit Windows for Viral Load Data

Nominal Visit	Nominal Study Day	Visit Window Study Day	
		Lower Limit	Upper Limit
Day 1/Baseline	1	1	1
Week 1	8	2	11
Week 2	15	12	18
Week 3	22	19	25
Week 4	29	26	32
Week 5	36	33	39
Week 6	43	40	46
Week 7	50	47	53
Week 8	57	54	60
Week 9	64	61	67
Week 10	71	68	74
Week 11	78	75	81
Week 12	85	82	88
Week 13	92	89	95
Week 14	99	96	127
Week 22	155	128	169
Week 26	183	>169	

Table 3. Analysis Visit Windows for Vital Sign Data

Nominal Visit	Nominal Study Day	Visit Window Study Day	
		Lower Limit	Upper Limit
Day 1/Baseline	1	1	1
Week 2	15	2	22
Week 4	29	23	36
Week 6	43	37	50
Week 8	57	51	64
Week 10	71	65	78
Week 12	85	79	92
Week 14	99	93	113

Week 18	127	114	141
Week 22	155	142	169
Week 26	183	>169	

Table 4. Analysis Visit Windows for ECG, Clinical Labs, and Physical Exam Data

Nominal Visit	Nominal Study Day	Visit Window Study Day	
		Lower Limit	Upper Limit
Day 1/Baseline	1	1	1
Week 2	15	2	22
Week 4	29	23	36
Week 6	43	37	50
Week 8	57	51	64
Week 10	71	65	78
Week 12	85	79	92
Week 14	99	93	141
Week 26	183	>141	

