^l Viral loads of BKV, AdV, CMV, JCV, and HHV-6 in plasma and of EBV in PCMBs will be measured weekly for adult patients and pediatric patients ≥ 12 years old after allogenic HCT conditioning during pre-screening period and screening period until treatment assignment, if possible. Pediatric patients < 12 years old will have only one blood draw during the Screening visit and will not have weekly blood draws during the screening period. Viral load testing should NOT be done on day of HCT during pre-screening. The results of the repeat analyses from the screening period must be available at the time of treatment assignment, unless the timing of the Screening Visit is 1 week or less before treatment administration. Results of central laboratory testing for viral load will be used for the purpose of determining eligibility/inclusion.

^m Adult patients and pediatric patients ≥ 12 years old only

Table 2: Schedule of Activities – Treatment -- Period 1 for Patients ≥12 Years of Age (Week 1 to 14, All Cohorts)

Time Period	Treatment Assignment	Study Drug Administration Day	Treatment Period													
			Wk 1	Wk 2	Wk 3	Wk 4	Wk 5	Wk 6	Wk 7	Wk 8	Wk 9	Wk 10	Wk 11	Wk 12	Wk 13	Wk 14
Study Day		1 ^a	8	14	21	28	35	42	49	56	63	70	77	84	91	98
Visit Window (Days)		NA ^b	±3	±5	±3	±5	±3	±5	±3	±5	±3	±5	±3	±5	±3	±3
Study Procedures																
Review of I/E criteria		X														
Prior & concomitant medications as well as conditioning regimen for HCT		X		X		X		X		X		X		X		X
Adverse events ^c		X		X		X		X		X		X		X		X
Physical examination ^d		X		X		X		X		X		X		X		X
Weight		X			X			X			X			X		X
Vital signs ^e		X		X		X		X		X		X		X		X
12-lead ECG ^f		X		X		X		X		X		X		X		X
Clinical labs ^g		X		X		X		X		X		X		X		X
Pregnancy test ^h		X		X		X		X		X		X		X		

Time Period	Treatment Assignment	Study Drug Administration Day	Treatment Period													
			Wk 1	Wk 2	Wk 3	Wk 4	Wk 5	Wk 6	Wk 7	Wk 8	Wk 9	Wk 10	Wk 11	Wk 12	Wk 13	Wk 14
Study Day		1 ^a	8	14	21	28	35	42	49	56	63	70	77	84	91	98
Visit Window (Days)		NA	±3	±5	±3	±5	±3	±5	±3	±5	±3	±5	±3	±5	±3	±3
Study Procedures																
BKV, AdV, CMV, JCV, and HHV-6 viral load ⁱ			X	X	X	X	X	X	X	X	X	X	X	X	X	X
EBV PCMBs ⁱ		X	X	X	X	X	X	X	X	X	X	X	X	X	X	X
Treatment Assignment ^j	X															
Virus-Specific T Cell Assessment ^k		X				X		X			X			X		X
Study treatment administration ^l		X		X		X		X		X		X		X		
Post infusion monitoring ^m		X		X		X		X		X		X		X		
Infection assessment ⁿ		X	X	X	X	X	X	X	X	X	X	X	X	X	X	X

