^aThe infection assessment will be performed for all patients who require either treatment for disease or initiation of preemptive therapy during both the primary study period and the follow-up period through Week 26 (Section 8.3). It is very important to ensure that all procedures, as outlined in the SoA, are performed immediately prior to the initiation of treatment of viral diseases or initiation of preemptive therapy (ie, on the day anti-viral therapy is initiated). Most importantly, a plasma sample for AdV, BKV, CMV, HHV-6, and JCV and a PBMC sample for EBV for PCR testing at the central laboratory should be collected. Patients who develop viral infections will continue to be followed in the study and complete all remaining visits through Week 26.

^oAssessment of quality of life (using FACT-BMT, EQ-5D-5L, EQ-5D-Y, EQ-5D-Y Proxy Version 1questionnaires, as age-appropriate) should be completed prior to any study procedures at this visit.

Table 4: Schedule of Activities: Short-Term Follow-Up--Period 2, All Ages (Weeks 18 to 26, All Cohorts)

Study Week	Week 18	Week 22	Week 26/ET ^a
Study Day	126	154	182
Visit Window (Days)	±3	±3	±3
Study Procedures			
Prior & concomitant medications	X	X	X
Adverse events ^b	X	X	X
Weight			X
Vital signs	X	X	X
12-lead ECG			X
Clinical Labs			X
BKV, AdV, CMV, JCV, and HHV-6 viral load ^c		X	X
EBV PCMBs ^d		X	
Virus-Specific T Cell assessment ^e	X	X	X
Infection assessment ^f	X	X	X
Quality of Life (FACT-BMT and EQ-5D-5L, EQ-5D-Y, EQ-5D-Y Proxy Version 1) ^g	X	X	X

Abbreviations: AdV = adenovirus; ALT = alanine aminotransferase; AST = aspartate aminotransferase; BKV = BK virus; CBC = complete blood count; CMV = cytomegalovirus; EBV = Epstein-Barr virus; ECG = electrocardiogram; ET = Early Termination Visit; GVHD = graft versus host disease; HHV-6 = human herpesvirus 6; JCV = JC virus; LFT = liver function test; PBMCs = peripheral blood mononuclear cells

Note: Visits may be done via a home health visit as agreed with the Sponsor. Please see the Study Manual for more information.

^aThe Early Termination Visit will be performed for all patients who are prematurely discontinued from the study up to Week 26. It is very important to ensure that all procedures are performed in such patients at this visit prior to discontinuing the patient from the trial. Most importantly, a plasma sample for AdV, BKV, CMV, HHV-6, and JCV and a PCMB sample for EBV for PCR testing at the central laboratory should be collected at this visit.

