3 STATISTICAL METHODOLOGY

3.1 General Considerations

3.1.1 *Study Day*

Study day will be calculated from the date of first dose of study drug, as actual visit date – first dose date + 1. The day of the first dose of study drug will be Day 1, and the day immediately before and after Day 1 will be Day -1 and Day 2.

3.1.2 *Analysis Visits*

Subject visits might not occur on protocol-specified days. Therefore, for the purpose of analysis, all scheduled, unscheduled, and early termination visits will be assigned to analysis visits according to the analysis windows ([Appendix 1](#)) based on study days. If there is more than 1 assessment in an analysis window, the assessment closest to the target day will be used in the analysis. If there are 2 assessments in a window equidistant from the target day, the later assessment will be used in the analysis.

3.1.3 *Definition of Baseline*

Baseline is defined as the last non-missing measurement prior to the first dose of study treatment. This can be on Day 1 as long as the measurement is taken prior to the first dose.

3.1.4 *Summary Statistics*

Summary statistics will be presented. Unless otherwise stated, continuous variables will be summarized using the number of non-missing observations, arithmetic mean, standard deviation, median, minimum, and maximum values as descriptive statistics. Categorical variables will be summarized using the frequency count and the percentage of patients in each category as descriptive statistics.

3.1.5 *Handling of Dropouts and Missing Data*

In general, data will be analyzed and presented as observed and will not be imputed for the analysis of efficacy and safety, unless otherwise specified.

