3.4.3 Exploratory Efficacy Endpoints

The exploratory efficacy endpoints are listed in Section 2.3.3.

The observed and change from baseline in QoL assessments will be summarized through Week 26. Listings will be provided for the QoL assessments.

Since most of the patients are undetectable, the number and percentage of patients with detectable viremia (i.e., \geq LLOQ) will be summarized at Week 14 as well as by visit and at any visit.

By-patient listing will be provided for AdV, BKV, CMV, EBV, HHV-6, and/or JCV viremia and QoL measures.

Subgroup analyses may be conducted for the efficacy endpoints by type (class I or II), the number of HLA matches, and letermovir treatment at Baseline.

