^l Viral loads of BKV, AdV, CMV, JCV, and HHV-6 in plasma and of EBV in PCMBs will be measured weekly for adult patients and pediatric patients ≥ 12 years old after allogeneic HCT conditioning during pre-screening period and screening period until treatment assignment, if possible. Pediatric patients < 12 years old will have only one blood draw during the Screening visit and will not have weekly blood draws during the screening period. Viral load testing should NOT be done on day of HCT during pre-screening. The results of the repeat analyses from the screening period must be available at the time of treatment assignment, unless the timing of the Screening Visit is 1 week or less before treatment administration. Results of central laboratory testing for viral load will be used for the purpose of determining eligibility/inclusion.

^m Adult patients and pediatric patients ≥ 12 years old only.

Table 6. Schedule of Activities: Treatment - Period 1 for Patients \geq 12 Years of Age (Week 1 to 14, All Cohorts)

Time Period	Treatment Assignment	Study Drug Administration Day	Treatment Period													
			Wk 1	Wk 2	Wk 3	Wk 4	Wk 5	Wk 6	Wk 7	Wk 8	Wk 9	Wk 10	Wk 11	Wk 12	Wk 13	Wk 14
Study Day		1 ^a	8	14	21	28	35	42	49	56	63	70	77	84	91	98
Visit Window (Days)		NA ^b	± 3	± 5	± 3	± 5	± 3	± 5	± 3	± 5	± 3	± 5	± 3	± 5	± 3	± 3
Study Procedures																
Review of I/E criteria		X														
Prior & concomitant medications as well as conditioning regimen for HCT		X		X		X		X		X		X		X		X
Adverse events ^c		X		X		X		X		X		X		X		X
Physical examination ^d		X		X		X		X		X		X		X		X
Weight		X				X				X				X		X
Vital signs ^e		X		X		X		X		X		X		X		X
12-lead ECG ^f		X		X		X		X		X		X		X		X
Clinical labs ^g		X		X		X		X		X		X		X		X
Pregnancy test ^h		X		X		X		X		X		X		X		
BKV, AdV, CMV, JCV, and HHV-6 viral load ⁱ		X	X	X	X	X	X	X	X	X	X	X	X	X	X	X
EBV PCMBs ^j		X	X	X	X	X	X	X	X	X	X	X	X	X	X	X
Treatment Assignment ^j	X															

Time Period	Treatment Assignment	Study Drug Administration Day	Treatment Period													
			Wk 1	Wk 2	Wk 3	Wk 4	Wk 5	Wk 6	Wk 7	Wk 8	Wk 9	Wk 10	Wk 11	Wk 12	Wk 13	Wk 14
Study Day		1 ^a	8	14	21	28	35	42	49	56	63	70	77	84	91	98
Visit Window (Days)		NA ^b	±3	±5	±3	±5	±3	±5	±3	±5	±3	±5	±3	±5	±3	±3
Study Procedures																
Virus-Specific T Cell Assessment ^k		X				X		X			X		X			X
Study treatment administration ^l		X		X		X		X		X		X		X		
Post infusion monitoring ^m		X		X		X		X		X		X		X		
Infection assessment ⁿ		X	X	X	X	X	X	X	X	X	X	X	X	X	X	X

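### The SAP viral-load windows file some on-schedule samples under another week, which affects the by-visit and Week 14 viremia summaries

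*SAP*

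**What the plan says.** SAP Section 3.1.2 states that "all scheduled, unscheduled, and early termination visits will be assigned to analysis visits according to the analysis windows". If several assessments share a window, the one closest to the target day is used, and a tie goes to the later one. Study day is counted from first dose: "The day of the first dose of study drug will be Day 1" (SAP Section 3.1.1).

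SAP Appendix 1, "Table 2. Analysis Visit Windows for Viral Load Data", puts Week 1 at Day 8 (window Days 2 to 11). Weeks 2 to 13 are at Days 15, 22 and so on to 92, each with a 7-day window. Week 14 is at Day 99 with a window of Days 96 to 127.

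The schedule in Protocol Section 1.3, repeated in SAP Appendix 2, puts Weeks 1 to 14 on Days "8 14 21 28 35 42 49 56 63 70 77 84 91 98". It permits 5 days either side at even Weeks 2 to 12, and 3 days either side at the odd weeks and Week 14.

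The windowed values feed the viral load and change from baseline over time (SAP Section 3.4.2). They also feed the number of patients with detectable viremia, which "will be summarized at Week 14 as well as by visit and at any visit" (SAP Section 3.4.3).

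**The concern.** A scheduled sample carries a visit label, but the SAP replaces it with the week into which its study day falls. Where the analysis windows do not match the permitted visit windows, a sample drawn fully on protocol is reported under a different week. If that week already has a sample closer to its target, the re-filed sample leaves the by-visit tables and its own week is blank.

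Two cases show this. Week 1 drawn on Day 8 and Week 2 drawn on Day 11 are both permitted, yet both fall in the Week 1 window. Day 8 is kept, Day 11 is not used, and Week 2 is empty. A Week 14 sample on permitted Day 95 is filed as Week 13. If Week 13 was drawn on Day 91, one day from its Table 2 target of 92, Day 95 is not used and Week 14 has no on-schedule value.

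The Week 14 window then runs 26 days past the last permitted visit day (127 − 101). An unscheduled or early-termination sample from Days 102 to 127 can fill the gap. Protocol Section 8.3.2 requires a central PCR sample whenever antiviral therapy starts, so such a sample may have been drawn because infection was suspected. In a descriptive cohort of 25 to 35 patients, a few such values can move a percentage visibly.

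**Working it through.** The documents state no misfiling rate, so there is no planned figure to reproduce.

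**Step 1: how the windows are built.** From Week 2 on, the Table 2 target is 7 × week + 1, and Weeks 2 to 13 have limits 3 days either side (Week 8: 57, Days 54 to 60). The Week 14 upper limit is the midpoint to Week 22: (99 + 155)/2 = 127. The schedule uses 7 × week from Week 2 on. Both use Day 8 for Week 1.

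**Step 2: file every permitted day by Table 2.**

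| Week | Permitted days | Table 2 window | Filed under another week |
|---|---|---|---|
| 1 | 5–11 | 2–11 | none (0 of 7) |
| 2 | 9–19 | 12–18 | 9, 10, 11, 19 (4 of 11) |
| 3 | 18–24 | 19–25 | 18 (1 of 7) |
| 4 | 23–33 | 26–32 | 23, 24, 25, 33 (4 of 11) |
| 13 | 88–94 | 89–95 | 88 (1 of 7) |
| 14 | 95–101 | 96–127 | 95 (1 of 7) |

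Weeks 6, 8, 10 and 12 repeat the Week 4 pattern, and Weeks 5, 7, 9 and 11 the Week 3 pattern.

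- Permitted days: 6 × 11 + 8 × 7 = 122.
- Filed elsewhere: 6 × 4 + 6 × 1 + 1 = 31, and 31/122 = 25.4%.
- Even Weeks 2 to 12: 24/66 = 36.4%. Odd Weeks 3 to 13: 6/42 = 14.3%.
- With Weeks 22 and 26 added (none misfiled): 31/136 = 22.8%.

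**Step 3: separate the two causes.** The permitted visit windows overlap. Days 9 to 11 belong to both Week 1 and Week 2 (3 days), and each of the 11 neighbouring pairs from Weeks 2/3 to Weeks 12/13 shares 2 days. That gives 3 + 11 × 2 = 25. Non-overlapping day windows can give each shared day to only one week, so at least 25 of 122 (20.5%) are misfiled whatever the centring. Moving the Table 2 windows one day earlier reaches exactly 25. The other 31 − 25 = 6 are Days 25, 39, 53, 67, 81 and 95. Each belongs to only one week in the schedule and goes to the preceding week because of the offset.

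**Step 4: from days to visits.** The documents give no distribution of visit timing, so these shares rest on assumptions.

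- Uniform within the permitted window: (6 × 4/11 + 7 × 1/7)/14 = 22.7% of visits.
- Triangular around the scheduled day: 7/36 at even weeks and 1/16 at the seven affected 3-day visits, so (6 × 7/36 + 7 × 1/16)/14 = 11.5%.
- Normal, with SD equal to half the half-width: 9.1%.
- If only 3 days either side were used at every visit, 13 of 98 days (13.3%) would be misfiled.

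**Step 5: children under 12.** In SAP Table 7, five of the six viruses are sampled after baseline at even Weeks 2 to 12 and Weeks 13 and 14. The count is (24 + 1 + 1)/(66 + 7 + 7) = 26/80 = 32.5% of permitted days.

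**The case against.** Filing by elapsed day is a legitimate choice, and the assigned week is often the nearer one. Of the 31 days, 18 lie closer to the scheduled day of the week that the SAP assigns, and one (Day 11) is a tie. Day 9, for example, is one day from Week 1's Day 8 and five from Week 2's Day 14. This stands: many of these samples are relabelled to a neighbouring time, not placed far from it.

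The Table 2 centring also has a rationale. With first dose on Day 1, 14 days later is Day 15, and all four Appendix 1 tables use 7 × week + 1 from Week 2 on. The schedule is irregular in having Week 1 on Day 8 but Week 2 on Day 14. This supports reconciling the two sets of days, without presuming that either is the error. It does not remove the effect, because sites work to the schedule.

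The long Week 14 window matters only when no nearer sample exists in it, since the closest-to-target rule applies and no viral load is scheduled at Week 18. For the five viruses sampled mainly at even weeks in young children, there is usually no competing odd-week sample, so a re-filed value is normally relabelled and not lost.

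A reader might infer more than the documents support:

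- That the analysis windows are narrower throughout. They are narrower only at even Weeks 2 to 12, equal at odd Weeks 3 to 13, and wider at Weeks 1, 14, 22 and 26.
- That the offset causes the whole 25%. It accounts for 6 of the 31 days.
- That a quarter of samples are misfiled or lost. The 25% is a share of permitted days, and a value is discarded only when two samples share a window.

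**Conclusion.** The concern holds in a limited form. Followed as written, SAP Section 3.1.2 and Table 2 put 31 of 122 permitted visit days in Weeks 1 to 14 (25%) under another week, 6 through the offset and 25 through overlap in the permitted visit windows. The share of actual visits depends on timing that the documents do not give: 22.7% if uniform, about 9 to 11% if clustered near target.

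The reach is the by-visit viral-load summaries and the detectable-viremia summaries, including the exploratory Week 14 endpoint. It does not extend to the primary or key secondary endpoint, which count infections and end-organ disease as determined by the investigators. A reader might expect the mean viral load (AUC divided by days) to be distorted too. The SAP does not say whether AUC uses actual sampling days or windowed visits, so that effect is unproven. The change is still worth making before database lock, because it keeps valid on-protocol samples at little cost.

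**What to change.** In SAP Section 3.1.2, file scheduled viral-load samples under their recorded visit, and use day windows only for unscheduled and early-termination samples. Recentring alone would leave 25 of 122 days misfiled, so this is the main step.

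Reconcile the Table 2 target days with the schedule, so that Days 95 to 101 all count as Week 14. End the Week 14 window close to the permitted visit window, and state that later unscheduled samples still count in the any-visit summary and the listings. State that AUC uses actual sampling days and all samples.

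Separately, the schedule gives the even-week dosing visits a 5-day tolerance, while its treatment footnote gives the dose interval a 3-day tolerance. These passages need reconciling.

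The cost is SAP wording and a small programming change. The downside is a few more missing Week 14 values, where a late sample would otherwise have filled the gap.

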Appendix 2 Schedule of Activities

Table 5. Schedule of Activities: Pre-screening Period and Screening Period (All Cohorts)

	Pre-screening Visit ^a	Pre-screening Period ^a	Screening Visit ^b	Screening Period ^b
Study Week	NA	Weekly Visits	Up to 6 weeks before Study Drug Administration	Weekly after Screening Visit until Study Drug Administration
Study Day	NA	NA	May be from Day -42 to Study Drug Administration Day	May be from Day -42 to Study Drug Administration Day
Visit Window (Days)	NA	±3	NA	±3
Study Procedures				
Informed consent/assent ^c	X		X	
I/E criteria	X ^d		X	
Demographics			X	
Medical history ^d			X	
Documentation of HLA typing ^e			X	
Prior and concomitant medications including conditioning regimen for HCT			X	X
Adverse events ^f			X	X
Complete physical examination			X	
Weight and height ^g			X	
Vital signs ^h			X	
12-lead ECG			X	
Clinical labs ⁱ			X	
Pregnancy test ^j			X	
Testing for HIV, HCV, HBV ^k			X	
BKV, AdV, CMV, JCV, EBV, and HHV-6 viral load ^l	X	X	X	X ^m

Abbreviations: AdV = adenovirus; ALT = alanine aminotransferase; AST = aspartate aminotransferase; β-HCG = beta human chorionic gonadotropin; BKV = BK virus; CBC = complete blood count; CMV = cytomegalovirus; EBV = Epstein-Barr virus; ECG = electrocardiogram; GGT = gamma- glutamyltransferase; HBV = hepatitis B virus; HCV = hepatitis C virus; HIV = human immunodeficiency virus; HHV-6 = human herpesvirus 6; HLA = human leukocyte antigen; I/E = inclusion and exclusion; JCV = JC virus; LFT = liver function test; NA = not applicable; PBMCs = peripheral blood mononuclear cells

Note: Visits may be done via a home health visit as agreed with the Sponsor. Please see the Study Manual for more information.

^a Adult patients and pediatric patients ≥ 12 years old may participate in an optional pre-screening period that may begin up to 4 weeks prior to administration of conditioning for HCT and continue until there is a decision on whether to screen for the study. Viremia testing during pre-screening will begin after HCT and will continue weekly, if possible. Pre- screening is not required for eligibility.

^b The Screening Visit could occur any time between the day of HCT and up to 42 (+7) days post-HCT. When this visit occurs during this time period may vary by patient depending upon when the decision is made to participate in the study.

^c Prior to conducting any study-related activities, written informed consent/assent to participate in the study must be provided by the patient and/or patient's guardian. The ICF for the pre-screening period is separate from the ICF that is signed at Screening Visit for study participation.

^d To include CMV sero status of both patient and HCT donor.

^e The HLA type of the patient and their HCT cell donor(s) will be obtained from the medical record.

^f Adverse events will be monitored and documented from signing of the ICF for study participation until study participation is complete.

^g Height and weight will be measured at screening. At later assessments during the Treatment Period, only weight will be assessed.

^h Includes body temperature, blood pressure, heart rate, O₂ saturation, and respiration rate and will be measured after resting for 5 minutes.

ⁱ Clinical laboratory assessments collected as part of standard of care may be used to fulfill these requirements. CBC must include differential and LFTs must include alkaline phosphatase, bilirubin (total and direct), GGT, AST, and ALT. Urinalysis must be performed. Laboratory safety evaluations (hematology, chemistry, and urinalysis) specified in the protocol will be performed prior to study therapy initiation. These samples will be sent to the appropriate central laboratory(ies) following the procedure(s) described in the study manual(s).

^j For female patients, at Screening a β -HCG blood test will be performed. A urine pregnancy test will also be performed at the site prior to study therapy initiation (SoA for Treatment Period, [Table 6](#)).

^k Serum will be screened for HIV, HBV, and HCV antibodies with reflex nucleic acid testing of plasma. Medical records of previous testing in the last 3-6 months may be used.

^l Viral loads of BKV, AdV, CMV, JCV, and HHV-6 in plasma and of EBV in PCMBs will be measured weekly for adult patients and pediatric patients ≥ 12 years old after allogeneic HCT conditioning during pre-screening period and screening period until treatment assignment, if possible. Pediatric patients < 12 years old will have only one blood draw during the Screening visit and will not have weekly blood draws during the screening period. Viral load testing should NOT be done on day of HCT during pre-screening. The results of the repeat analyses from the screening period must be available at the time of treatment assignment, unless the timing of the Screening Visit is 1 week or less before treatment administration. Results of central laboratory testing for viral load will be used for the purpose of determining eligibility/inclusion.

^m Adult patients and pediatric patients ≥ 12 years old only.

Table 6. Schedule of Activities: Treatment - Period 1 for Patients \geq 12 Years of Age (Week 1 to 14, All Cohorts)

Time Period	Treatment Assignment	Study Drug Administration Day	Treatment Period													
			Wk 1	Wk 2	Wk 3	Wk 4	Wk 5	Wk 6	Wk 7	Wk 8	Wk 9	Wk 10	Wk 11	Wk 12	Wk 13	Wk 14
Study Day		1 ^a	8	14	21	28	35	42	49	56	63	70	77	84	91	98
Visit Window (Days)		NA ^b	± 3	± 5	± 3	± 5	± 3	± 5	± 3	± 5	± 3	± 5	± 3	± 5	± 3	± 3
Study Procedures																
Review of I/E criteria		X														
Prior & concomitant medications as well as conditioning regimen for HCT		X		X		X		X		X		X		X		X
Adverse events ^c		X		X		X		X		X		X		X		X
Physical examination ^d		X		X		X		X		X		X		X		X
Weight		X				X				X				X		X
Vital signs ^e		X		X		X		X		X		X		X		X
12-lead ECG ^f		X		X		X		X		X		X		X		X
Clinical labs ^g		X		X		X		X		X		X		X		X
Pregnancy test ^h		X		X		X		X		X		X		X		
BKV, AdV, CMV, JCV, and HHV-6 viral load ⁱ		X	X	X	X	X	X	X	X	X	X	X	X	X	X	X
EBV PCMBs ^j		X	X	X	X	X	X	X	X	X	X	X	X	X	X	X
Treatment Assignment ^j	X															

Time Period	Treatment Assignment	Study Drug Administration Day	Treatment Period													
			Wk 1	Wk 2	Wk 3	Wk 4	Wk 5	Wk 6	Wk 7	Wk 8	Wk 9	Wk 10	Wk 11	Wk 12	Wk 13	Wk 14
Study Day		1 ^a	8	14	21	28	35	42	49	56	63	70	77	84	91	98
Visit Window (Days)		NA ^b	±3	±5	±3	±5	±3	±5	±3	±5	±3	±5	±3	±5	±3	±3
Study Procedures																
Virus-Specific T Cell Assessment ^k		X				X		X			X		X			X
Study treatment administration ^l		X		X		X		X		X		X		X		
Post infusion monitoring ^m		X		X		X		X		X		X		X		
Infection assessment ⁿ		X	X	X	X	X	X	X	X	X	X	X	X	X	X	X
Quality of Life (FACT-BMT, EQ- 5D-5L, EQ-5D-Y, EQ-5D-Y Proxy Version 1) ^o		X				X			X				X			X

Abbreviations: AdV = adenovirus; ALT = alanine aminotransferase; AST = aspartate aminotransferase; ; β-HCG = beta human chorionic gonadotropin; BKV = BK virus; CBC = complete blood count; CMV = cytomegalovirus; EBV = Epstein-Barr virus; ECG = electrocardiogram; ET = Early Termination Visit; GGT = gamma-glutamyl transferase; GVHD = graft versus host disease; HBV = hepatitis B virus; HCV = hepatitis C virus; HIV = human immunodeficiency virus; HHV-6 = human herpesvirus 6; I/E = inclusion and exclusion; IVIG = intravenous immunoglobulin; JCV = JC virus; LFT = liver function test; NA = not applicable; PBMC = peripheral blood mononuclear cell; SoA = Schedule of Activities; VST = virus-specific T cell; Wk = week

Note: Visits may be done via a home health visit as agreed with the Sponsor. Please see the Study Manual for more information.

^a Unless noted otherwise, Day 1 procedures must be performed within 72 hours prior to study treatment administration.

^b Dosing day may be up to +7 days with Sponsor approval.

^c Adverse event monitoring should include the collection of all adverse events through the treatment period in all patients, including those who have discontinued study treatment but are continuing in the study. For patients who have discontinued, only drug-related SAEs and SAEs leading to death will be collected until Week 26.

^d After treatment assignment, a targeted physical exam may be performed if a patient has any complaints. Post-HCT, the skin should be examined, even if the patient has no complaint, for evidence of rash/acute skin GVHD.

^e Includes body temperature, blood pressure, heart rate, O₂ saturation, and respiration rate and will be measured after resting for 5 minutes. After treatment assignment, vital signs should be performed during and after infusions and if targeted physical examination is performed.

^f Performed within 1 hour after study treatment administration and at the end of study or early termination visit, which are listed in the SoA for the Short-term Follow-up period ([Table 8](#)).

^g Clinical laboratory assessments collected as part of standard of care may be used to fulfill these requirements. CBC must include differential and LFTs must include alkaline phosphatase, bilirubin (direct and indirect); GGT, AST, and ALT. Urinalysis must be performed. Laboratory safety evaluations (hematology, chemistry, and urinalysis) specified in the protocol will be performed prior to study drug initiation. These samples will be sent to the appropriate central laboratory(ies) following the procedure(s) described in the study manual(s).

^h For female patients, a urine pregnancy test will be performed at the site prior to study therapy initiation. If the urine pregnancy test result is negative, the patient will be eligible for treatment assignment and the remainder of the Day 1 testing/procedures will be performed. If the urine pregnancy result is positive, the patient must not be assigned to treatment and should reflex to a β-HCG blood test before screen failing. A urine pregnancy test will be performed prior to each treatment for female patients who are of childbearing potential.

ⁱ Viral loads of AdV, BKV, CMV, JCV, and HHV-6 in plasma and of EBV in PCMBs will be measured. Additional post-infusion samples may be collected, as clinically indicated. If patient develops any clinically significant infection of AdV, BKV, CMV, EBV, HHV-6, or JCV at any point during the study periods, infection assessments should be followed prior to initiating standard of care therapy.

^j Patients in Cohort OL will be assigned to ALVR105. Patients in Cohorts A and B will be randomized to either ALVR105 or placebo based upon the last viral load assessed and within 7 days of randomization. Treatment assignment will be about 2 to 3 days before Day 1.

^k Patient peripheral blood mononuclear cells will be assessed for the presence of virus-reactive T cells using enzyme-linked immunospot.

^l All patients will receive infusions of either ALVR105 or placebo. Patients will receive the same [REDACTED] dose for patients ≤40 kg or [REDACTED] dose for patients >40 kg for all infusions of ALVR105, administered at a dose interval of every 14 days (±3 days). Placebo infusions will be administered every other week in order to maintain the blind. As GVHD and CRS are a theoretical safety concern associated with administration of third-party allogeneic T cells, the incidence and severity of GVHD and CRS will be monitored during the study. No patients will be permitted to receive a subsequent infusion of ALVR105 if they develop new onset GVHD Grade >2 or worsening of GVHD (ie, relative to baseline GVHD at the time of enrollment into the study) at the proposed time for infusion of the next dose, or if they develop CRS Grade >2; if any patient develops GVHD or CRS, the Medical Monitor should be contacted immediately, and the patient treated per standard of care. If discontinued for CRS or GVHD these participants should be followed up to resolution of symptoms. Patients may resume treatment only with consultation and agreement between the Medical Monitor and the Investigator. If possible, IVIG and ALVR105 should not be administered on the same day.

^m Patients will be monitored closely and must remain in the clinic for ≥1 hour after the end of each infusion. Vital signs, including body temperature, heart rate, O₂ saturation, respiration rate, and blood pressure, will be measured at the end of the infusion, and at 15, 30, 45, and 60 minutes after the end of the infusion. Patients must also remain on continuous pulse oximetry for ≥30 minutes after the end of the infusion. Post-infusion monitoring should be completed for all infusions of study treatment.

ⁿ The infection assessment will be performed for all patients who require either treatment for disease or initiation of preemptive therapy during both the primary study period and the follow-up period through Week 26. It is very important to ensure that all procedures, as outlined in the SoA, are performed immediately prior to the initiation of treatment of viral diseases or initiation of preemptive therapy (ie, on the day anti-viral therapy is initiated). Most importantly, a plasma

sample for AdV, BKV, CMV, HHV-6, and JCV and a PBMC sample for EBV for PCR testing at the central laboratory should be collected. Patients who develop viral infections will continue to be followed in the study and complete all remaining visits through Week 26.

◦ Assessment of quality of life (using FACT-BMT, EQ-5D-5L, EQ-5D-Y, EQ-5D-Y Proxy Version 1questionnaires, as age-appropriate) should be completed prior to any study procedures at this visit.

Table 7. Schedule of Activities: Treatment - Period 1 for Patients <12 Years of Age (Week 1 to 14, All Cohorts)

Time Period	Treatment Assignment	Study Drug Administration Day	Treatment Period													
			Wk 1	Wk 2	Wk 3	Wk 4	Wk 5	Wk 6	Wk 7	Wk 8	Wk 9	Wk 10	Wk 11	Wk 12	Wk 13	Wk 14
Study Day		1 ^a	8	14	21	28	35	42	49	56	63	70	77	84	91	98
Visit Window (Days)		NA ^b	±3	±5	±3	±5	±3	±5	±3	±5	±3	±5	±3	±5	±3	±3
Study Procedures																
Review of I/E criteria		X														
Prior & concomitant medications as well as conditioning regimen for HCT		X		X		X		X		X		X		X		X
Adverse events ^c		X		X		X		X		X		X		X		X
Physical examination ^d		X		X		X		X		X		X		X		X
Weight		X			X				X				X		X	
Vital signs ^e		X		X		X		X		X		X		X		X
12-lead ECG ^f		X		X		X		X		X		X		X		X
Clinical labs ^g		X		X		X		X		X		X		X		X
Pregnancy test ^h		X		X		X		X		X		X		X		
BKV, CMV, JCV, and HHV-6 viral load ⁱ		X		X		X		X		X		X		X	X	X
EBV PBMCs ^j		X		X		X		X		X		X		X	X	X
AdV viral load		X	X	X	X	X	X	X	X	X	X	X	X	X	X	X
Treatment Assignment ^j	X															
Virus- Specific T Cell Assessment ^k		X				X		X			X			X		X
Study treatment administration ^l		X		X		X		X		X		X		X		

Time Period	Treatment Assignment	Study Drug Administration Day	Treatment Period													
			Wk 1	Wk 2	Wk 3	Wk 4	Wk 5	Wk 6	Wk 7	Wk 8	Wk 9	Wk 10	Wk 11	Wk 12	Wk 13	Wk 14
Study Day		1 ^a	8	14	21	28	35	42	49	56	63	70	77	84	91	98
Visit Window (Days)		NA ^b	±3	±5	±3	±5	±3	±5	±3	±5	±3	±5	±3	±5	±3	±3
Study Procedures																
Post infusion monitoring ^m		X		X		X		X		X		X		X		
Infection assessment ⁿ		X	X	X	X	X	X	X	X	X	X	X	X	X	X	X
Quality of Life (FACT- BMT, EQ-5D-5L, EQ-5D-Y, EQ-5D-Y Proxy Version 1) ^o		X					X			X				X		X

Abbreviations: AdV = adenovirus; ALT = alanine aminotransferase; AST = aspartate aminotransferase; ; β-HCG = beta human chorionic gonadotropin; BKV = BK virus; CBC = complete blood count; CMV = cytomegalovirus; EBV = Epstein-Barr virus; ECG = electrocardiogram; ET = Early Termination Visit; GGT = gamma-glutamyl transferase; GVHD = graft versus host disease; HBV = hepatitis B virus; HCV = hepatitis C virus; HIV = human immunodeficiency virus; HHV-6 = human herpesvirus 6; I/E = inclusion and exclusion; IVIG = intravenous immunoglobulin; JCV = JC virus; LFT = liver function test; NA = not applicable; PBMC = peripheral blood mononuclear cell; SoA = Schedule of Activities; VST = virus-specific T cell; Wk = week

Note: Visits may be done via a home health visit as agreed with the Sponsor. Please see the Study Manual for more information.

^a Unless noted otherwise, Day 1 procedures must be performed within 72 hours prior to study treatment administration.

^b Dosing day may be up to +7 days with Sponsor approval.

^c Adverse event monitoring should include the collection of all adverse events through the treatment period in all patients, including those who have discontinued study treatment but are continuing in the study. For patients who have discontinued, only drug-related SAEs and SAEs leading to death will be collected until Week 26.

^d After treatment assignment, a targeted physical exam may be performed if a patient has any complaints. Post-HCT, the skin should be examined, even if the patient has no complaint, for evidence of rash/acute skin GVHD.

^e Includes body temperature, blood pressure, heart rate, O₂ saturation, and respiration rate and will be measured after resting for 5 minutes. After treatment assignment, vital signs should be performed during and after infusions and if targeted physical examination is performed.

^f Performed within 1 hour after study treatment administration and at the end of study or early termination visit, which are listed in the SoA for the Short-term Follow-up period (Table 8).

